2. PURPOSE AND RATIONALE

The purpose of Allergan's Savella Pregnancy Registry (Registry) is to monitor pregnancies exposed to Savella (milnacipran HCl) to determine the risk of birth defects. Because Savella is commonly used among reproductive age women, this pregnancy registry has been established to prospectively assess the birth outcomes of babies born to women that are exposed to Savella during pregnancy. The lack of human fetal safety data concerning this product makes such a monitoring system an important component of epidemiologic research on the safety of Savella. Due to the lack of human data regarding fetal safety, the Registry is primarily exploratory.

The primary objective of the Savella Pregnancy Registry is:

• To estimate the prevalence of major congenital anomalies among offspring of women exposed to Savella during pregnancy.

The secondary objectives are

- To estimate the prevalence of full-term live births (≥37 weeks), pre-term live births (<37 weeks), recognized spontaneous abortions, stillbirths, induced abortions (elective and therapeutic), chromosomal abnormalities, and minor congenital anomalies
- 2) To summarize
- Serious pregnancy complications and maternal adverse events
- Adverse pregnancy outcomes
- Serious adverse outcomes observed during the first year of life in infants born from exposed pregnancies, including alterations in fetal/infant growth, presence of functional deficits, biochemical abnormalities, transient or infectious conditions, symptoms of poor neonatal adaptation (i.e., neonatal withdrawal), and persistent pulmonary hypertension of the newborn

3. **REGISTRY DESIGN**

This is a prospective, observational, exposure-registration and follow-up registry of women exposed to Savella during pregnancy. The Registry is strictly observational; the schedule of patient visits and treatment regimens are at the discretion of the treating physician. HCPs submit patient data that are routinely collected and documented in the patient's medical record.

4. **REGISTRY POPULATION**

The Registry population includes women with any Savella exposure during pregnancy, defined as exposure on or after the first day of the LMP. Women must be \geq 18 years of age and reside in the US.

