5.6 Follow-up Evaluation by Pediatrician for Live Births

5.6.1 Timing of Pediatric Follow-Up

If a live birth occurs, the mother is asked to give consent for the infant's pediatrician to provide follow-up information. If consent is obtained, the pediatrician completes the **Pediatric Follow-Up Form** immediately after birth, at 4 months, and 12 months of age.

Pediatric Follow-up Form

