5.6.2 Information Collected at Pediatric Follow-up

Infant at outcome

- Date of follow-up evaluation
- Current age of infant (at the time of assessment)
- Gender
- Gestational age at birth
- APGAR scores at birth
- Birth weight, length, head circumference and corresponding population-based percentiles
- Birth defect(s) and details, if noted
 - Type of birth defect(s)
 - Attribution to Savella drug therapy
 - Other factors that might have contributed to the outcome
 - Defect absent/present on pre- or post-natal test
- Chromosomal abnormalities and details, if noted
- Immediate post-natal health problems requiring resuscitation, admission to the neonatal intensive care unit (NICU)
- Medications
- Surgical interventions required of pre-term infants
- Other serious infant adverse outcomes noted on physical examination
 - Evidence of alterations in fetal/infant growth (e.g., intrauterine growth restricted, small for gestational age, etc.)
 - Presence of functional deficit (e.g., poor muscle tone, abnormal reflexes)
 - Presence of biochemical abnormality
 - Presence of transient or infectious conditions
 - Symptoms of poor neonatal adaptation (i.e., neonatal withdrawal)
 - Persistent pulmonary hypertension of the newborn

Infant at 4 and 12 months

- Date of follow-up evaluation
- Current age of infant (at the time of assessment)
- Birth weight, length, head circumference and corresponding population-based percentiles
- Birth defect(s) detected since last assessment and details, if noted
 - Type of birth defect(s)
 - Attribution to Savella drug therapy
 - Other factors that might have contributed to the outcome
 - Defect absent/present on pre- or post-natal test
- Chromosomal abnormalities and details, if noted
- Medications
 - Other serious infant adverse outcomes noted on physical examination

- Evidence of alterations in infant growth
- Presence of functional deficits
- Developmental delays

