6.2.7 Losses to Follow-Up (LTFU)

A prospective report meeting the minimum criteria for enrollment but for which follow-up information on the pregnancy outcome (live birth, fetal loss, etc.) is never obtained, is unavailable, and/or where the indication of a birth defect is designated as "unknown" is considered "pregnancy lost to follow-up". For the infant portion of the Registry, live born infants where pediatric follow-up information is never obtained, is unavailable, and/or where infant status is designated as "unknown" is considered "infant lost to follow-up". Section 6.3 provides a complete description of the follow-up process. Losses to follow-up are tallied in the Registry Interim Reports and the Final Report, but are not included in the statistical analyses.

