8.5.3 Adverse Pregnancy Outcomes

Overall and by-stratum point estimates of rates and 95% confidence intervals will be calculated for the following outcomes:

- Spontaneous abortions
- Stillbirths
- Induced abortions (overall and elective or therapeutic)
- Minor congenital anomalies,

Other adverse pregnancy outcomes among pregnancies exposed to Savella and their live births during the first year of life will be summarized as counts and percentages of the total number of prospective evaluable outcomes. Summaries will also be presented by subgroups including maternal age at conception (<25, 25-35, >35), family history of birth defects, smoking status, and alcohol use during pregnancy. Additional subgroups may be analyzed if deemed appropriate and necessary given the sample size. These other adverse pregnancy outcomes include:

- Functional deficits
- Alterations in fetal growth
- Transient or infectious conditions
- Biochemical abnormalities
- Pre-term infants with findings that persist and require surgical intervention

Strata are comprised by earliest trimester of exposure and potentially other variables as appropriate given the sample size, such as maternal age, history of birth defects, lifestyle variables, comorbidities, and concomitant drug exposures.

All chromosomal abnormalities, whether classified as a birth defect or other adverse outcome, will be displayed in a separate listing.

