14. DISCONTINUATION OF REGISTRY

This Registry could consider discontinuation after one of more of the following occurs:

- Sufficient information has accumulated to meet the scientific objectives of the Registry;
- Other methods of gathering appropriate information become achievable or are deemed preferable; or
- The feasibility of collecting sufficient information diminishes to unacceptable levels because of low exposure rates, poor enrollment, or losses to follow-up.

The Registry's Scientific Advisory Committee will review the above criteria on a yearly basis and assess the need to discontinue the Registry as currently designed. Allergan will not discontinue the registry until they have consulted with the FDA to ensure that the FDA has reviewed the final study report and determined that the study data has met the study objectives and the obligations of the Post Marketing Requirements.

At the time of discontinuation, the PI will notify the IRB of the Pregnancy Registry discontinuation and/or termination. These considerations are documented in the FDA Guidance document, *Establishing Pregnancy Exposure Registries* (FDA, 2002).

REFERENCES

- American College of Obstetrics and Gynecology (ACOG). Use of psychiatric medications during pregnancy and lactation. ACOG Practice Bulletin Number 92. *Obstet Gynecol.* 2008;111:1001-20.
- Centers for Disease Control and Prevention. Metropolitan Atlanta Congenital Defects Program 6-Digit code defect list. To access an electronic copy of the code list, go to http://www.cdc.gov/ncbddd/bd/macdp_resources.htm and click on the 3rd bullet.
- Centers for Disease Control and Prevention. Update on overall prevalence of major birth defects Atlanta, Georgia, 1978-2005. *MMWR*. 2008; 57:1-5.

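### Infant loss to follow-up is not tied to the birth, 4-month or 12-month contact, and Section 8.5.3 divides first-year outcomes by all evaluable outcomes, so infants unseen after birth count as event-free

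*Protocol*

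**What the plan says.** Protocol Section 5.6.1 has the pediatrician complete the same form "immediately after birth, at 4 months, and 12 months of age", provided the mother consents. Section 5.6.2 lists the items for the birth contact separately from those for 4 and 12 months. The later contacts ask, among other things, for "Birth defect(s) detected since last assessment and details, if noted".

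Section 6.2.7 defines infant loss once for the whole infant part of the Registry. The label attaches to "live born infants where pediatric follow-up information is never obtained, is unavailable", with one further condition: "and/or where infant status is designated as 'unknown' is considered 'infant lost to follow-up". The consequence follows: "Losses to follow-up are tallied in the Registry Interim Reports and the Final Report, but are not included in the statistical analyses".

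Section 8.5.3 sets the denominator. Other adverse outcomes among exposed pregnancies and their "live births during the first year of life will be summarized as counts and percentages of the total number of prospective evaluable outcomes". The objective served, in Section 2, is to summarize "Serious adverse outcomes observed during the first year of life in infants born from exposed pregnancies".

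**The concern.** The objective covers a year and the schedule has three contacts, but the loss rule has one status with no contact or age attached. There is no category for partial follow-up and no tally by contact. If the birth form comes back and the 4- and 12-month forms do not, pediatric information has been obtained and the infant's status was known at birth. On the natural reading that infant need not be tallied as lost.

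Two things are at stake. The infant loss figure in the Interim and Final Reports can be lower than the share of infants without 12-month data. And because the 8.5.3 denominator does not require a later form, infants nobody observed after birth are counted as free of later events, which moves the percentage toward no risk. Section 14 names "low exposure rates, poor enrollment, or losses to follow-up" among the feasibility grounds for discontinuation, so the loss figure may also inform that yearly review.

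**Working it through.** **The plan's own figures (Section 8.4).** Expected live births: 350 × 0.62 × 0.90 = 195.3, against 196 stated. Exact one-sample binomial with n = 196 and baseline 2.78%: reject at 11 or more cases (upper tail 0.0221); power at 6.95% is 80.7%, or 80.2% with n = 195. The stated 80% is reproduced, and nothing below changes it. The 10% loss in that section is loss of pregnancies; the protocol states no infant loss rate and no first-year event rate.

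**Which outcomes are exposed.** Section 8.5.3 lists five: functional deficits, alterations in fetal growth, transient or infectious conditions, biochemical abnormalities, and pre-term infants with persistent findings needing surgery. Section 5.6.2 collects all five at birth. Only functional deficits is expressly listed again at 4 and 12 months, so it is the main 8.5.3 item that can be missed when later forms are absent.

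**Illustration.** Assumptions, none from the protocol: 196 live births; 10% with no pediatric form; a further 20% with the birth form only; later events are missed wherever later forms are missing; the true later-event risk is 5.0% in every infant. Read literally, the 8.5.3 denominator also includes outcomes other than live births; I use live births so that only the missing forms drive the result.

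- Tallied as lost, if the rule means no form at all: 196 × 0.10 = 19.6, about 20 (10%).
- Without 12-month data: 196 × 0.30 = 58.8, about 59 (30%).
- Later events observed: 196 × 0.70 × 0.05 = 6.86, against 196 × 0.05 = 9.8 occurring.
- Over all live births: 6.86 / 196 = 3.5%.
- With the no-form infants excluded, as 6.2.7 directs for losses: 6.86 / 176.4 = 3.9%.
- Over infants with later forms: 6.86 / 137.2 = 5.0%.

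**Range.** With 5% to 20% having no form and a further 10% to 40% the birth form only, the tally is 10 to 39 infants (5% to 20%), while 29 to 118 (15% to 60%) lack a 12-month form. The reported later-event proportion is 0.40 to 0.85 of its true value over all live births. It is 0.50 to 0.89 of its true value when only the no-form infants are removed.

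**Outcomes partly seen at birth are diluted less.** If every infant has a birth form, a share L of events arises later and a share R of later forms returns, the reported rate is 5% × [(1 − L) + L × R]. With R = 0.7:

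- L = 0.8: 5% × 0.76 = 3.8%.
- L = 0.5: 5% × 0.85 = 4.25%.

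**The case against.** The strongest reply is that 6.2.7 has three conditions, not one. Besides information never obtained, it covers information that is unavailable and status that is unknown. It points to Section 6.3, where follow-up is chased request by request, so staff could class an infant with no 12-month form as lost under the existing words. This stands in part: a reader might infer that an infant is lost only if no form ever arrives, and the text does not support that. What it supports is a rule that is ambiguous by contact. The other reading is no better, because 6.2.7 then takes the infant out of the statistical analyses with no provision for the birth-form data already collected.

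Other limits also stand:

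- No text says that a birth-form-only infant counts as followed for a year. That is inferred from the missing rule and the 8.5.3 denominator.
- The dilution comes mainly from that denominator; changing 6.2.7 alone would not remove it.
- Developmental delay and infant growth might seem to be affected through 8.5.3, but they are not in its list. Developmental milestones fall under Section 8.5.4, which fixes no denominator.
- A reader might infer that the tally would show almost no infant loss. Pediatric contact needs maternal consent, infants with no form are tallied on any reading, and no return rates are given.
- Section 14 neither cites the infant tally nor sets a threshold on it.

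It may also be said that denominators for descriptive tables belong in the SAP. That is usually so, but here the protocol itself fixes both the loss definition and the denominator. An SAP that follows it inherits the problem. The general remark on under-ascertainment in Section 7.1.2 and the discussion of pregnancy losses in Section 8.6 do not address incomplete infant follow-up.

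**Conclusion.** The point holds as a defect of definition and denominator. As written, an infant observed only at birth need not appear in the loss tally and counts as event-free in the first-year percentages of 8.5.3. The bias is toward no risk for later-arising outcomes, in that list chiefly functional deficits. Its size cannot be derived from the protocol; 5.0% shown as 3.5% is an illustration that assumes 30% of infants lack later forms and equal risk in all infants.

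A reader might extend this to the primary result. The documents do not support that: Section 8.5.1 keeps prospectively enrolled pregnancies with an outcome in the risk calculation whatever their later infant loss status. Defects first found after birth may still be missed in infants without later forms, but the loss label does not cause that. The outcomes concerned are secondary and descriptive.

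**What to change.** - In 6.2.7, record infant follow-up status separately at birth, 4 months and 12 months, and tally losses at each contact.
- In 8.5.3, replace the single denominator for infant outcomes with the number of live-born infants who have a form for the contact concerned. Report per contact and print that number beside each percentage.
- Do not add infants to a later contact's denominator only because they had an earlier event. That would keep early cases without later forms while dropping event-free infants without later forms, and so push the rate up.

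No new data are needed: the evaluation table in Section 5 already separates the birth contact from the 4- and 12-month contacts, and 5.6.2 records the date of each evaluation. The cost is smaller denominators and a higher stated infant loss figure. The new percentages still assume that infants with later forms resemble those without, and the tally by contact lets a reader judge how much rests on that.

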6.2.8 Identification of Duplicate Registry Reports

Reports received by the Registry are reviewed for possible duplicate reporting. On receipt of a registration form from an HCP, the report is compared to other reports to determine if the same report was received previously. If a duplicate is not identified, the report is entered into the database. If a duplicate is later identified, the case reported earliest or the one with the most complete data is maintained as the valid case and updated with any data from the other report not already captured. The duplicate report is flagged and designated as "invalid", with reason of "duplicate report".

6.3 Follow-up Process

6.3.1 Attempts to Obtain the Follow-up Information

The standard process for obtaining follow-up at interim reporting periods is to notify the reporter by telephone that a letter with the appropriate follow-up data forms are being sent. The reporter is asked to complete and return it to the Registry or provide the data by phone. If the data forms are not returned in one month the reporter is contacted 3 times (every 2 weeks) by telephone. If no response is received, a final letter is sent encouraging return of data forms. All follow-up attempts are documented, and all appropriate reporters (healthcare professionals, patients, alternate contacts) are contacted according to the follow-up plan outlined above.

6.3.2 Follow-up Process for Resolution of Information

If there are outstanding questions, discrepancies between the registration and follow-up forms, or there are missing data, the query resolution process is as follows: either a hard copy of the data resolution form (DRF) is sent to the provider or the provider is contacted by phone. Three subsequent attempts, as necessary, are made every 2 weeks via mail, e-mail, fax or phone call. If no further information is obtained on an otherwise evaluable case, the discrepant information in the data fields may be left blank, identified as "unspecified", or on a case-by-case basis a determination of discrepant information made by the principal investigator (e.g., determination of partially illegible word or illogical year).

6.4 Calls to the Registry

All incoming and outgoing calls are tracked by the Research Specialist (RS) to monitor the source, type, purpose of the call, and whether or not further activity is needed to resolve the reason for the call.

7. OUTCOME CLASSIFICATION, EVALUATION AND MONITORING

7.1 Definitions

7.1.1 Pregnancy Outcome

Pregnancy outcomes are classified into one of the following mutually exclusive categories:

- Live birth full-term (≥ 37 weeks)
- Live birth pre-term (<37 weeks)
- Stillbirth
- Spontaneous abortion
- Induced abortion
 - Therapeutic
 - Elective
- Ectopic pregnancy
- Molar pregnancy
- Maternal/fetal death

Definitions of the individual outcome categories are located in the Glossary beginning on page 35.

7.1.2 Birth Defect

The Registry adopts the term "birth defect" for an abnormality usually referred to as a "congenital anomaly" and defines birth defect as follows:

• Any major structural or chromosomal defect diagnosed with signs/symptoms, using the CDC MACDP classification of birth defects (CDC, 1998).

On a case-by-case basis, subject to independent review, clusters of two or more minor abnormalities may in combination constitute a birth defect, even if the outcome of each event alone would not constitute a birth defect according to the MACDP classification. Defining two or more minor defects as a birth defect case is used to increase the sensitivity of pregnancy databases (Scheuerle and Covington, 2004). The presence of multiple minor defects has been shown to increase the likelihood that a major defect or syndrome exists (Leppig et al, 1987, Holmes et al, 1987). To maintain as much consistency with the CDC birth defect surveillance system as possible without missing a potential signal, only cases meeting the MACDP criteria and those with at least two minor defects are included for analysis. Cases with two minor anomalies will trigger further investigation by the registry's birth defect evaluator; the determination of the birth defect evaluator would then decide whether the specifics of any particular case merit its inclusion as a birth defect case. All infants with three or more minor anomalies will be counted as a birth defect case.

The inclusion of cases with minor defects is a conservative approach with the potential to inflate point estimates and enhance signal detection. Individual minor abnormalities are listed in the report but are not included in the analysis of defects.

Under certain circumstances, structural or chromosomal defects detected in the prenatal evaluation of a pregnancy or in the gross or pathologic examination of an abortus, fetus, or deceased infant, that would not otherwise be included in the primary analysis following normal protocol procedures, may be included in a subsequent analysis to increase the sensitivity of Registry monitoring. Such determinations are made on a case-by-case basis and are subject to independent review.

The CDC guidelines disqualify as birth defects:

- Conditions that are attributed to prematurity alone, such as patent ductus arteriosus (PDA), patent foramen ovale (PFO), and inguinal hernias. If these conditions are present in infants born < 37 weeks gestational age or if gestational age is unavailable, weighing < 2500 grams, they are not considered birth defects. If these conditions are present in infants born ≥ 37 weeks gestational age, they are considered birth defects.
- Infants with only transient or infectious conditions, or biochemical abnormalities, are classified as being without birth defects unless there is a possibility that the condition reflects an unrecognized birth defect.

The Registry focuses on birth defect data detected and reported during pregnancy and up to one year of age for live born infants. Most major structural defects and clusters of minor abnormalities are readily apparent during this time frame. However, under ascertainment of birth defects is possible. The Registry does update case reports if information is received on any birth defect diagnosed with signs/symptoms occurring up to six years of age. However, this information is not systematically collected. The Registry collects information on minor abnormalities, transient or infectious conditions, and biochemical abnormalities that reporting clinicians deem important.

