8.3 Comparison Groups

Given the inherent difficulties in identifying an appropriate comparison group, several different methods may be used to review the data for any signals of teratogenicity. First, assuming a sufficient sample size is attained, the prevalence of birth defects in this Registry is compared to the prevalence observed in the MACDP, a population-based birth defects surveillance system that is administered by CDC (1998). The total prevalence of birth defects identified among births from 1968 through 2003 was 2.67% (Correa et al., 2007). However, the MACDP recognizes that prior to 1973 the annual prevalence was lower because of incomplete case ascertainment and that since 1973 the total defect prevalence has remained stable with only minimal year-to-year variation. The most recent five-year prevalence rate of 2.78% (6945 birth defect cases in 249,999 live births) from 1999 to 2003 is deemed the most appropriate comparator rate for this Registry (Correa et al., 2007). The baseline prevalence rate for specific birth defects varies.

The methods and patient population in this Registry differ from those used in the MACDP and therefore it may not be the most appropriate comparator. The primary objectives of MACDP are to monitor, regularly and systematically, births of malformed infants for changes in incidence or other unusual patterns suggesting environmental influences and develop a case registry for use in epidemiological studies. MACDP actively searches for birth defects among the 50,000 annual births to residents of metropolitan Atlanta's five counties and abstracts medical records at all Atlanta obstetric hospitals, Atlanta pediatric referral hospitals, genetics labs, and vital records (Correa-Villasenor et al., 2003). MACDP data has been used as a comparator group when examining birth defects for several existing pregnancy registries (acyclovir; sumatriptan; lamotrigine; and zidovudine) (Honein et al., 1999).

As a second method of analysis, the prevalence of birth defects among women in the Registry may be compared to the prevalence observed in published studies of pregnant women exposed to other drugs for similar indications if available at that time.

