8.4 Sample Size

The Registry seeks to enroll approximately 350 prospective pregnancies. According to data from the general population, approximately 62% of clinically recognized pregnancies results in a live birth (FDA, 2002). Based on data from similar pregnancy registries, 10% are lost to follow-up. Therefore, the resulting number of live births is expected to be 196.

Compared to a baseline frequency of total birth defects of 2.78% from the MACDP (Correa et al., 2007), a sample size of 196 exposed live births provides 80% power to detect an overall prevalence rate of birth defects of at least 6.95%, which corresponds to a 2.5-fold increase over baseline. This estimate is based on the one-sample exact binomial method using a 2-sided type I error rate of 5%. Sample size considerations are based on the one-sample exact binomial test, although 95% confidence intervals (CI) will be used, rather than hypothesis testing, as the primary method to guide comparative assessments to the MACDP rate. For specific defects, the power to detect an increased risk varies depending on the frequency of the defect in the population and the evolving size of the exposed group.

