8.5 Data Analysis

8.5.1 Birth Defects

For the primary analysis, the prevalence of birth defects reported to the Registry in the evaluable population is calculated by dividing the number of birth defects (i.e., the number of pregnancy outcomes occurring at or after 20 weeks gestation with a noted birth defect) by the total number of live births in the evaluable population. Pregnancy losses with reported birth defects occurring at or after 20 weeks gestation are included in the numerator of the estimate of risk for birth defects to increase sensitivity and to allow for comparison with the MACDP which calculates rates using this convention. A secondary analysis is conducted including pregnancy losses with reported birth defects occurring at any gestational age in the calculation of risk. An additional secondary analysis will be performed that only includes birth defects that are noted from ultrasound examinations (pre-natal or post-natal). Birth defects will be reported by outcome (live birth (overall and full-term or pre-term)), stillbirth, induced abortion (elective or therapeutic) and trimester of exposure. All defects detected <20 weeks of gestation will be described in the report. Additionally, birth defects noted by non-HCP reports will be reported descriptively.

Calculations of 95% confidence intervals (two-sided) for individual birth defect rates are based on the exact method using binomial probability distribution. The prevalence in exposed cases is compared with the observed prevalence in the MACDP (Correa et al., 2007). In addition, one-sample binomial tests at the two-sided 0.05 level are used to test the association of elevated levels of major birth defects in pregnancy exposures to Savella by comparing the observed proportion of birth defects in the Registry with rates from the MACDP.

Enrolled pregnancies that are LTFU without pregnancy outcome, as defined in section 6.2.6, will be enumerated in the interim/final report, but will not be included in the

calculation of risk. Prospectively enrolled pregnancies with an outcome will be included in the calculation of risk regardless of whether they are subsequently designated as infant LTFU.

If feasible, comparisons between the Registry and an appropriate external comparison group will be examined.

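### The birth-defect rate compared with MACDP's 2.78% also counts clusters of minor anomalies, so the comparison is not like-for-like and its error rate is not controlled at the stated level

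*Protocol*

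**What the plan says.** The primary objective (Protocol, section 2) concerns major congenital anomalies; minor anomalies are a separate secondary objective.

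Section 7.1.2 defines a birth defect by the MACDP classification and then widens it. A cluster of minor abnormalities may count "even if the outcome of each event alone would not constitute a birth defect according to the MACDP classification". Two minor anomalies go to the birth defect evaluator, who decides. For larger clusters no decision is needed: "All infants with three or more minor anomalies will be counted as a birth defect case". The section names MACDP cases and cases with two or more minor defects as two groups and takes both into the analysis. It is open about the effect: "The inclusion of cases with minor defects is a conservative approach with the potential to inflate point estimates and enhance signal detection". On data capture it says: "The Registry collects information on minor abnormalities, transient or infectious conditions, and biochemical abnormalities that reporting clinicians deem important".

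Section 8.5.1 then states: "The prevalence in exposed cases is compared with the observed prevalence in the MACDP". It adds a one-sample binomial test at the two-sided 0.05 level, described as a test on major birth defects. The comparator is fixed in section 8.3: "The most recent five-year prevalence rate of 2.78% (6945 birth defect cases in 249,999 live births) from 1999 to 2003".

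The same section 8.5.1 puts losses at or after 20 weeks into the numerator partly so that the rate can be compared with MACDP. Its secondary analyses cover losses at any gestational age and defects noted on ultrasound. Neither is a MACDP-criteria-only rate. The Glossary presents the whole definition, clusters included, as conforming to CDC guidelines.

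**The concern.** The observed rate and the reference rate are built from different case definitions. Any infant who qualifies only through a cluster adds to the registry's numerator. On section 7.1.2's own division of the case set, such an infant has no counterpart among the cases behind 2.78%. Taken alone, this pushes the comparison upward.

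The protocol's other choices show that comparability was wanted: section 8.5.1 follows MACDP's convention for losses, and section 7.2 has the evaluator classify by MACDP. The cluster rule works against that aim, and no planned analysis removes its effect.

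The 2.78% figure is the only comparator the protocol fixes, in a registry that answers a post-marketing requirement to compare exposed with unexposed pregnancies (Background). With about five cases expected, one or two infants can decide whether the interval excludes 2.78%. A report could then show an apparent excess without the reader being able to tell how much comes from the wider definition.

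**Working it through.** **Inputs from the protocol.** Null rate 2.78% (section 8.3: 6945/249,999 = 2.778%). Alternative 6.95% = 2.5 × 2.78%, stated power 80%, two-sided 5% one-sample exact binomial (section 8.4). Enrolment: "The Registry seeks to enroll approximately 350 prospective pregnancies", with 62% live births and 10% lost. Size: "Therefore, the resulting number of live births is expected to be 196". Arithmetic: 350 × 0.62 × 0.90 = 195.3, close to the stated 196. I use n = 196.

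**Reproducing the plan's power.** Let X ~ Bin(196, p).
- The smallest r with P(X ≥ r | p = 0.0278) ≤ 0.025 is r = 11, where the upper tail is 0.0221.
- The lower rejection region is X = 0, with probability 0.0040. Equal-tail total size is 0.0221 + 0.0040 = 0.0261.
- P(X ≥ 11 | p = 0.0695) = 0.807, so the stated 80% reproduces.
- The minimum-likelihood exact test rejects at X ≤ 1 or X ≥ 11. Its size is 0.0484 and its power is also 0.807.

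**The same boundary governs the interval.** Ten cases (10/196 = 5.10%) give an exact lower 95% limit of 2.47%, below 2.78%. Eleven (5.61%) give 2.83%, above it. The expected count under the null is 196 × 0.0278 = 5.4, and each extra case adds 1/196 = 0.51 percentage points.

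**Adding cluster-only cases.** Let a be the background prevalence of infants who qualify only through a cluster. The protocol gives no figure, so every value of a above zero is an assumption. With no drug effect the counted rate is p = 0.0278 + a, while the null tested stays at 0.0278.

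| a (points, assumed) | p | Expected cluster-only infants (196 × a) | Upper tail P(X ≥ 11) | Total size, equal-tail | Total size, minimum-likelihood |
|---|---|---|---|---|---|
| 0 | 2.78% | 0 | 2.2% | 2.6% | 4.8% |
| 0.10 | 2.88% | 0.20 | 2.8% | 3.1% | 4.98% |
| 0.25 | 3.03% | 0.49 | 3.8% | 4.0% | 5.5% |
| 0.50 | 3.28% | 0.98 | 6.0% | 6.1% | 7.1% |
| 1.00 | 3.78% | 1.96 | 12.6% | 12.6% | 13.0% |

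**Thresholds.** Solving for a:
- The upper tail passes 2.5% at about 0.055 points.
- Total size passes 5% at about 0.11 points with the minimum-likelihood test (196 × 0.0011 = 0.2 infants).
- Total size passes 5% at about 0.38 points with the equal-tail test (196 × 0.0038 = 0.7 infants).

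**An opposing bias.** Section 8.6 says that enrolling after a normal prenatal test may lower the observed risk. Assume, for illustration, that this removes 10% of MACDP-type cases, so p = 0.0278 × 0.90 + a. The equal-tail size is then 3.8% at a = 0.5 points and 8.6% at a = 1.0 point.

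**The case against.** The strongest reply is that the widening is deliberate and disclosed. Section 7.1.2 gives its reason: clusters make an underlying major defect or syndrome more likely, and sensitivity matters in surveillance. Section 2 calls the registry mainly exploratory. Section 8.2 makes descriptive statistics primary and disclaims inference from intervals, section 8.4 puts intervals ahead of tests, and section 8.3 doubts that MACDP is the best comparator. All of this stands, and it rules out treating the cluster rule as a hidden error. It does not make the comparison like-for-like: the interval comparison turns on the same 11-case boundary as the test, the caveat in section 8.3 does not name clusters, and section 8.5.1 still fixes a 0.05 test.

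Three stronger readings are tempting, and the document does not support them.

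- *That the type I error exceeds 5%.* This depends on a cluster-only prevalence the protocol does not give. The equal-tail test has slack (2.6% against 5%) and stays within 5% up to about 0.4 points.
- *That the registry rate is inflated overall.* Section 8.6 names a downward bias, section 7.1.2 admits possible under-ascertainment, and MACDP searches records actively while this registry relies on voluntary reports. Recording minor abnormalities at clinicians' discretion may also mean fewer clusters, not more. The net sign is unknown.
- *That an excess could come entirely from the definition.* Moving the expected count from 5.45 to 11 would need 5.55 cluster-only infants (5.55/196 = 2.8 points), well beyond the range shown. A cluster-only infant could, however, be the one that moves the count from 10 to 11.

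Section 7.1.2 says only that each anomaly *alone* falls outside the MACDP classification, and the Glossary aligns the whole definition with the CDC. How MACDP itself treats multiple minor anomalies cannot be checked here. But section 7.1.2 also lists clusters apart from MACDP cases and warns of inflation, which makes sense only if the two sets differ.

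**Conclusion.** The point holds in a limited form. The rate set against 2.78% has a wider case definition than its comparator, this component acts upward, and no planned analysis isolates it. The stated error level is therefore not controlled. Whether it is actually breached depends on an unreported cluster-only prevalence and on the form of exact test.

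The size and threshold figures assume 196 live births, a true MACDP-type rate of 2.78% with no drug effect and, except in the opposing-bias illustration, no other bias. Since the opposing biases are unquantified, they cannot be counted on to cancel the effect; they are a further reason to remove a mismatch that can be removed. This is a cheap improvement to how the comparison reads. It does not invalidate the registry.

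**What to change.** - In section 8.5.1, and in the matching synopsis text, state that the prevalence used for the confidence-interval comparison and the binomial test against 2.78% counts only cases meeting MACDP criteria.
- Report the expanded prevalence, clusters included, alongside it with its own exact interval. Label it a signal-detection sensitivity analysis that is not like-for-like with MACDP. It need not be kept away from the 2.78% figure, provided the label is there.
- Reconcile section 7.1.2 (which cases enter which analysis) with the Glossary, so that the cluster rule is shown as the registry's own extension or, if it truly is part of the CDC definition, section 7.1.2 says so.

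The cost is a few sentences in three or four places. No new data are needed, since the evaluator already classifies each case by MACDP conventions (section 7.2). The downside is that cluster-only cases no longer count toward the formal comparison. They remain in the report and in the Scientific Advisory Committee's review, so signal detection is not lost.
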